8.3.4.2 Relationship to Study Intervention

For each reported adverse reaction, the PI or designee must assess the relationship of the event to each study product using the following guideline:

- Related – There is a temporal relationship between the study intervention and event, and the AE is known to occur with the study intervention or there is a reasonable possibility that the study intervention caused the AE. Reasonable possibility means that there is evidence to suggest a causal relationship between the study intervention and the AE.
- Not Related – There is not a reasonable possibility that the administration of the study intervention caused the event, there is no temporal relationship between the study intervention and event onset, or an alternate etiology has been established.

8.3.5 Time Period and Frequency for Event Assessment and Follow-Up

For this study, all Grade 3 and 4 AEs, and all SAEs occurring from the time the first study product is initially given on Day 1 through the Day 29 visit will be documented, recorded, and reported.

8.3.5.1 Investigator Reporting of AEs

Information on AEs will be recorded on the appropriate CRF. All clearly related signs, symptoms, and procedures performed because of an AE should be grouped together and recorded as a single diagnosis. If the AE is a laboratory abnormality that is part of a clinical condition or syndrome, it should be recorded as part of the syndrome or diagnosis rather than the individual laboratory abnormality. If a clinical site does not have an upper limit of normal (ULN) or a lower limit of normal (LLN) for a graded laboratory parameter (e.g., INR), the site will follow the reference range as outlined in the MOP.

Each AE will also be described in terms of duration (start and stop date), severity, association with each study product (i.e., baricitinib/po placebo versus dexamethasone/IV placebo versus remdesivir infusion), the action(s) taken, and outcome.

Any new infection that occurs on study, regardless of infecting agent (i.e., viral or non-viral) will be captured if it is a Grade 3 or 4 AE or SAE. Completion of the Infection Follow-up eCRF page is required for each infection reported as an adverse event or SAE with site of infection and source of culture provided, if available. The purpose is to document the occurrence of new infections by type of infection and not the duration of the new infections. Therefore, capture the first positive result(s) for the new infection (e.g., blood or urine culture, molecular diagnostic test result, etc.); there is no need to capture repeatedly positive results unless there is a new pathogen identified from the same site (e.g., blood) during the infection event. The sponsor will identify infections considered to be opportunistic based on Winthrop et al. 2015.

8.3.6 Serious Adverse Event Reporting

8.3.6.1 Investigators Reporting of SAEs

Any AE that meets a protocol-defined criterion as an SAE that is judged to be related to any study product must be submitted within 24 hours of site awareness on an SAE form to the DMID Pharmacovigilance Group, at the following address:

DMID Pharmacovigilance Group
Clinical Research Operations and Management Support (CROMS)
[name]
[name]
SAE Hot Line: [name] (US) or [contact] (outside US)
SAE [contact] (US) or [contact] (outside US)
SAE Email Address: [contact]

Other supporting documentation of the event may be requested by the DMID Pharmacovigilance Group and should be provided as soon as possible. The DMID Medical Monitor will review and assess the SAE for regulatory reporting and potential impact on study subject safety and protocol conduct. At any time after completion of the study, if the site PI or appropriate sub-investigator becomes aware of an SAE that occurred during the subject's participation in the study, the site PI or appropriate sub-investigator will report the event to the DMID Pharmacovigilance Group.

SAEs that are judged to be not related to study product are still captured on the AE case report form, but do not require separate reporting to the DMID Pharmacovigilance Group.

8.3.6.2 Regulatory Reporting of SAEs

Following notification from the site PI or appropriate sub-investigator, DMID, as the IND Sponsor, will report any SUSAR in an IND safety report to the FDA and will notify all participating site PIs as soon as possible. DMID will report to the FDA any unexpected fatal or life-threatening suspected adverse reaction as soon as possible, but in no case later than 7 calendar days after the Sponsor's initial receipt of the information. If the event is not fatal or life-threatening, the IND safety report will be submitted within 15 calendar days after the Sponsor determines that the information qualifies for reporting as specified in 21 CFR Part 312.32. Relevant follow up information to an IND safety report will be submitted as soon as the information is available. Upon request from the FDA, DMID will submit to the FDA any additional data or information that the agency deems necessary, as soon as possible, but in no case later than 15 calendar days after receiving the request.

SAEs that are not SUSARs will be reported to the FDA at least annually in a summary format which includes all SAEs.

Sites may have additional local reporting requirements (to the IRB and/or national regulatory authority).

8.3.7 Reporting of Pregnancy

Pregnancy is not an AE. However, any pregnancy that occurs during study participation should be reported to the Sponsor on the appropriate CRF. Pregnancy should be followed to outcome.

8.4 Unanticipated Problems

8.4.1 Definition of Unanticipated Problems

- Unexpected in terms of nature, severity, or frequency given (a) the research procedures that are described in the protocol-related documents, such as the IRB-approved research protocol and informed consent document; and (b) the characteristics of the subject population being studied;
- Related to participation in the research (meaning there is a reasonable possibility that the incident, experience, or outcome may have been caused by the procedures involved in the research); and
- Suggests that the research places subjects or others at a greater risk of harm (including physical, psychological, economic, or social harm) than was previously known or recognized.

8.4.2 Unanticipated Problem Reporting

To satisfy the requirement for prompt reporting, all UPs will be reported using the following timeline:

- UPs that are SAEs will be reported to the IRB and to the Statistical and Data Coordinating Center (SDCC)/study Sponsor within 24 hours of the investigator becoming aware of the event per the above described SAE reporting process.
- Any other UP will be reported to the IRB and to the SDCC/study Sponsor within 3 days of the investigator becoming aware of the problem.

9. STATISTICAL CONSIDERATIONS

9.1 Statistical Hypotheses

The null hypothesis of no difference in the proportion of patients surviving without requiring invasive mechanical ventilation between baricitinib/remdesivir and dexamethasone/remdesivir will be tested using a superiority test.

A key secondary hypothesis will test whether the distribution of the 8-point ordinal scale at Day 15 differs between baricitinib/remdesivir and dexamethasone/remdesivir. For this key secondary hypothesis, the parameter of interest is the “common odds ratio,” which quantifies the shift in the severity distribution resulting from treatment. The null hypothesis to be tested is that the odds of improvement on the ordinal scale is the same for the control and experimental treatment arms (i.e., the common odds ratio is 1). An odds ratio greater than 1 quantifies an improvement in disease severity for the experimental treatment relative to its control. It is worth noting that, for large sample sizes, the test based on the proportional odds model is nearly the same as the Wilcoxon rank sum test.

9.2 Sample Size Determination

The primary hypothesis will be a test of the difference in proportions surviving without requiring invasive mechanical ventilation between the two treatment arms by Day 29. Estimating the expected treatment effect of baricitinib relative to dexamethasone is difficult given the

Appendix D - ACTT-4: Baricitinib/Remdesivir vs Dexamethasone/Remdesivir

differences between the ACTT-2 and RECOVERY studies as discussed above. In [Table 9](#), the first row of treatment effects is based on estimates from the ACTT-2 and RECOVERY results amongst the cohort that most closely resembles the ACTT-4 target population (those in ordinal 5 and 6). In the second row, the relative findings were changed to assume a gradual improvement in standard of care. This corresponds to a sample size of 1382 subjects. Sample size calculations were based on an exact unconditional score test of proportions using StatXact v11.1.0. Assuming 8% lost to follow-up, the sample size is planned to be approximately 1500 subjects.

The remaining lines demonstrate the power of the proposed sample size. There is good power of this trial for multiple scenarios unless the proportions surviving without invasive mechanical ventilation is much higher than anticipated (thought to be unlikely) or the difference in the proportions is smaller than anticipated (possible, but difficult to anticipate given the data available).

The formal analyses will be based on Kaplan-Meier estimates of the proportion of patients surviving without mechanical ventilation by Day 29 using a large sample normal approximation with Greenwood's variance formula. Accordingly, power for the final analysis is assumed to be equal or slightly higher than the power for the exact score as seen below.

Table 9: Sample size estimates and study power.

| | Total Sample Size | Proportion Dex Arm Surviving Through Day 29 Without Mechanical Ventilation | Proportion Bari Arm Surviving Through Day 29 Without Mechanical Ventilation | Power (unconditional exact score) | Power (KM + Greenwood) |
|--|-------------------|--|---|-----------------------------------|------------------------|
| - Baricitinib from ACTT-2 (OS 5 and 6) - Dexamethasone relative efficacy (only those on oxygen) from RECOVERY applied to ACTT-2 placebo arm | 1342 | 0.814 | 0.87 | 80.9% | 80.6% |
| Estimate of the above proportion applied to current outcomes given gradual improvement in care | 1382 | 0.85 | 0.9 | 80% | 80.5% |
| | | | | | |
| Other scenarios showing study power for the sample size of 1382 | 1382 | 0.9 | 0.95 | 94.5% | 94.9% |
| | 1382 | 0.9 | 0.925 | 37.0% | 37.5% |
| | 1382 | 0.85 | 0.925 | 99.4% | 99.4% |
| | 1382 | 0.8 | 0.875 | 96.6% | 96.6% |
| | 1382 | 0.8 | 0.85 | 68.2% | 68.9% |

Note: two-sided type I error rate 5%; Exact unconditional score test of proportions.

9.3 Populations for Analyses

Appendix D - ACTT-4: Baricitinib/Remdesivir vs Dexamethasone/Remdesivir

The primary analysis will be based on an intention-to-treat population, including all subjects randomized. Safety analyses will be based a modified intent-to-treat population consisting of all subjects who received at least one dose of any investigational product.

An Endpoint Review Committee consisting of the DMID MO, her designees and the blinded statistical team may review endpoints, medications, deviations, and other special cases where expert opinion is requested for handling complicated cases.

9.4 Statistical Analyses

9.4.1 General Approach

This is a double-blind, placebo controlled randomized trial testing a superiority hypothesis with a two-sided type I error rate of 5%. Secondary hypotheses have been ordered according to relative importance, with one key secondary hypothesis highlighted. These will be described according to the appropriate summary statistics (e.g., proportions for categorical data, means, medians for time-to-event data) and 95% confidence intervals.

A statistical analysis plan will be developed and filed with the study sponsor prior to unblinding of study and database lock.

9.4.2 Analysis of the Primary Efficacy Endpoint

The primary efficacy analysis is a test of superiority of the proportion invasive mechanical ventilation free survival between the two treatment arms at Day 29. The test statistic will be a large sample test of the difference in Kaplan-Meier based estimates of the 28-day probability of mechanical ventilation free survival with a two-sided type I error rate of 0.05. The test of difference will assume asymptotic normality and use Greenwood's variance formula. (44)

If null hypothesis for the overall population is rejected, the analysis will proceed to test the null hypothesis within each baseline ordinal scale subgroup following the strategy described below.

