9.4.2 Analysis of the Primary Efficacy Endpoint

The primary efficacy analysis is a stratified log-rank test, where stratification is according to baseline disease severity as defined by ordinal scale. Deaths will be considered as never recovering and censored at Day 29. In ACTT-3, the analyses conducted will depend on the results from ACTT-1 according to [Table 4](#).

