6.3 Measures to Minimize Bias: Randomization and Blinding

6.3.1 Randomization

Randomization will be stratified by:

- Site
- Severity of illness at enrollment (by ordinal scale)
 - Hospitalized, on non-invasive ventilation or high flow oxygen devices, OR
 - Hospitalized, requiring supplemental oxygen

The randomization procedure will be described in the MOP.

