9.4.3 Analysis of the Secondary Endpoint(s)

- 1) The ordinal scale at Day 15 will be used to estimate a proportional odds model within different categories of the ordinal scale at baseline. The hypothesis test will perform a strata- adjusted test to evaluate whether the common odds ratio for treatment is equal to one. The distribution of severity results will be summarized by treatment arm as percentages. There will be efforts to minimize loss to follow-up. However, small amounts of missing data may occur. In such cases, outcomes may be imputed based on rules described in the SAP. Sensitivity analyses will evaluate the impact of making different assumptions about missing observations. These analyses will be defined in the SAP.
- 2) Differences in time-to-event endpoints (e.g., time to recovery or time to at least a one category improvement in ordinal scale, time to death) by treatment will be summarized with Kaplan-Meier curves and 95% confidence bounds, using the Fine-Gray approach for competing events when appropriate.
- 3) Analysis of mortality data will be evaluated using a Cox proportional hazards model.

4) Desirability of outcomes response (DOOR). A revised ordinal scale has been constructed to incorporate SAEs. SAE may be related or unrelated to study product. Any SAE occurring after study product administration through Day 15 (or through Day 29) will be counted:

| |
|---|
| 1- Recovered (OS 1,2,3) |
| 2- Improved by at least 1 OS from baseline & no SAE |
| 3- Improved by at least 1 OS from baseline & SAE |
| 4- No change in OS from baseline & no SAE |
| 5- No change in OS from baseline & SAE |
| 6- Worsened by at least 1 OS from baseline |
| 7- Death (OS 8) |

*OS = ordinal scale score based on the 8-point scale

This DOOR scale will be evaluated at Day 15 and Day 29, and between arm differences will be tested using a Mann-Whitney U-statistic.

5) Change from baseline in ordinal scale at specific time points will be summarized by proportions (e.g., proportion who have a 1-, 2-, 3-, or 4-point improvement or 1-, 2-, or 3-point worsening).

6) Duration of event (e.g., duration of mechanical ventilation) will be summarized according to median days with quartiles and mean with SD.

7) Binary data (e.g., incidence of new oxygen use) will be summarized as a percent with 95% confidence intervals. Comparisons between arms will be presented as differences in proportions with 95% confidence intervals.

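### ACTT-4: the primary test does not use the baseline-severity stratum that randomization uses; adding it would recover about 1 to 1.5 points of power at no cost

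*Protocol*

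**What the plan says.** Protocol Appendix D, section 9.4.2, defines the ACTT-4 primary test as "a large sample test of the difference in Kaplan-Meier based estimates of the 28-day probability of mechanical ventilation free survival", two-sided at 0.05. On the variance it adds: "The test of difference will assume asymptotic normality and use Greenwood's variance formula". No stratum or covariate is named. Baseline ordinal score enters only afterwards: "If null hypothesis for the overall population is rejected, the analysis will proceed to test the null hypothesis within each baseline ordinal scale subgroup".

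Appendix D, section 6.3.1, stratifies randomization by site and by severity at enrollment, with two levels: non-invasive ventilation or high-flow oxygen (score 6) and supplemental oxygen (score 5).

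Elsewhere the protocol says so when it wants the stratum in a test:
- For the ACTT-4 key secondary (Appendix D, section 9.4.3): "The hypothesis test will perform a strata- adjusted test to evaluate whether the common odds ratio for treatment is equal to one".
- For ACTT-3 (Appendix C, section 9.4.2): "The primary efficacy analysis is a stratified log-rank test, where stratification is according to baseline disease severity as defined by ordinal scale".

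Appendix D, section 9.2, Table 9, sizes ACTT-4 for the unstratified test: 1382 subjects, 0.85 against 0.90, and 80.5% power by Kaplan-Meier with Greenwood variance.

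**The concern.** Allocation stratified by a prognostic factor keeps that factor nearly balanced between arms, so chance imbalance in severity contributes almost nothing to the true sampling variance of the treatment difference. Greenwood's formula applied to each whole arm does not know this and still counts the spread between the score 5 and score 6 event rates as noise. The reported standard error is therefore larger than the true one, the confidence interval is wider than it need be, and the test runs below its nominal level.

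What is at stake is efficiency in a trial planned with no margin above 80% power. Under section 9.4.9 the primary test is the gate to every later test in the fixed sequence, and under section 9.4.2 to the tests within each baseline score. A narrow miss on the primary blocks all of them.

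**Working it through.** **Inputs**
- Design (section 9.2, Table 9): ventilation-free survival 0.85 and 0.90, total 1382, so 691 per arm; two-sided 5%; 1:1 allocation (section 6.1).
- Stratum mix, from ACTT-2 (Appendix D, Table 2): score 5, 287 + 276 = 563; score 6, 104 + 113 = 217. Score 6 share = 217/780 = 27.8%, taken as 28%.
- Prognostic strength (Table 2, 28-day mortality). Control: (0.129/0.871)/(0.047/0.953) = 3.0. Baricitinib: (0.074/0.926)/(0.019/0.981) = 4.1.
- **Assumed:** the odds ratio of failure (ventilation or death), score 6 against score 5. The protocol gives no such figure. I take 3 to 4 from mortality as the guide and 8 as an outer case.

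**Step 1. Reproduce the stated power.** Without censoring, Greenwood reduces to p(1 − p)/n.

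SE(unstratified) = √[(0.85 × 0.15 + 0.90 × 0.10)/691] = √(0.2175/691) = 0.01774

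Power = Φ(0.05/0.01774 − 1.96) = Φ(0.858) = 80.5%, as Table 9 states.

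**Step 2. Stratified variance.** Hold each arm's overall failure rate at 0.15 and 0.10, solve for the stratum rates f5 and f6 at the assumed odds ratio, and use

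SE(stratified) = √{[V(dex) + V(bari)]/691}, where V = 0.72 f5(1 − f5) + 0.28 f6(1 − f6) in each arm.

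**Step 3. Compare like with like.** Under stratified allocation the true spread of the difference is SE(stratified), whichever test is used. So:
- True power, unstratified test = Φ{[0.05 − 1.96 × SE(unstratified)]/SE(stratified)}
- Power, stratified test = Φ{0.05/SE(stratified) − 1.96}
- True two-sided error, unstratified test = 2{1 − Φ[1.96 × SE(unstratified)/SE(stratified)]}, with failure 0.125 in both arms
- Equivalent saving in subjects = 1 − [SE(stratified)/SE(unstratified)]²

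| Failure odds ratio, score 6 : 5 | 3 | 4 | 8 |
|---|---|---|---|
| Dex f5 / f6 | 0.106 / 0.263 | 0.094 / 0.294 | 0.067 / 0.364 |
| Bari f5 / f6 | 0.069 / 0.181 | 0.060 / 0.203 | 0.041 / 0.253 |
| V(dex) + V(bari), against 0.2175 | 0.2100 | 0.2053 | 0.1906 |
| SE(stratified) | 0.01743 | 0.01724 | 0.01661 |
| Unstratified SE too large by | 1.8% | 2.9% | 6.8% |
| True error of unstratified test | 4.6% | 4.4% | 3.7% |
| True power, unstratified | 80.9% | 81.1% | 82.0% |
| Power, stratified | 81.8% | 82.7% | 85.3% |
| Gain in points | 0.9 | 1.5 | 3.3 |
| Equivalent saving of 1382 | 3.4% (48) | 5.6% (77) | 12.4% (171) |

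Example at odds ratio 4: (0.05 − 0.03477)/0.01724 = 0.883, giving 81.1%; 0.05/0.01724 − 1.96 = 0.940, giving 82.7%.

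**Step 4. Checks.** Simulation at odds ratio 4 (400,000 replicates, 691 per arm, balanced within stratum) gave power 81.2% unstratified and 82.8% stratified, with error rates 4.4% and 5.1%. With no prognostic effect both tests gave 5.1%, so that small excess comes from the normal approximation, not from stratifying. Over score 6 shares of 20% to 50% and odds ratios of 2 to 8, stratified power was 80.9% to 85.5% against a true 80.6% to 82.1% unstratified. At odds ratio 1 the gain is zero.

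**The case against.** The strongest reply is that nothing here is an error. The unstratified test is valid and, if anything, conservative. The trial was sized for exactly that test, and Table 9's power reproduces. Choosing a simpler statistic and paying for it in sample size is a legitimate design choice. All of that stands, and it is why the point is about efficiency only.

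A second reply is that stratum weights are ordinary SAP content, and main protocol section 9 leaves details to the SAP. This stands in part: an SAP could supply the stratification. But section 9.4.2 does not leave the method open. It names both the statistic and the variance, and the same protocol states adjustment explicitly for the key secondary and for the ACTT-3 primary.

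A third reply is that those comparisons prove little, being a proportional odds model and a log-rank test on other endpoints, and that the primary endpoint is also examined within each baseline score. Fair: the comparison shows a difference without a stated reason, not a contradiction. The within-score tests are follow-on tests and do not sharpen the overall one.

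Three stronger readings are tempting but unsupported:
- A reader might measure the gain from the nominal 80%. That overstates it, because the unstratified test's true power under stratified randomization is already about 81%.
- A reader might assume stratum rates such as 0.93/0.72 or 0.95/0.65. These imply failure odds ratios of 5.2 and 10.2, while the only stratum evidence in the protocol, mortality, gives 3.0 to 4.1.
- A reader might call baseline score the strongest predictor of ventilation or death. Table 2 compares it with no other predictor; it supports strongly prognostic for death and no more.

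**Conclusion.** The point holds as a free improvement. The primary test as written leaves out a prognostic randomization stratum, so its standard error is too large: by about 2% to 3% on plausible assumptions, with a true error rate of about 4.6% to 4.4%. Stratifying would gain about 1 to 1.5 points of power, equivalent to about 50 to 75 of 1382 subjects, and about 3 points at an odds ratio of 8.

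The direction is certain if score 6 carries a higher risk of ventilation or death than score 5. The size is not. It rests on the ACTT-2 mix carrying over to ACTT-4, on mortality odds ratios standing in for those of the composite endpoint, and on no censoring. Stratification by site was not modelled.

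A reader might infer that the trial is underpowered or its type I error inflated. Neither follows: the error rate stays below 5% and the planned power is met.

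**What to change.** In Appendix D, section 9.4.2, define the primary statistic as the stratum-weighted difference:
- estimate the Kaplan-Meier difference in 28-day ventilation-free survival separately within baseline scores 5 and 6;
- combine as D = Σ w_k D_k, with w_k the share of all randomized subjects in stratum k;
- take Var(D) = Σ w_k² (sum of the two arms' Greenwood variances in stratum k), and test Z = D/√Var(D).

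Use the same statistic at the interim look if section 9.4.6.2 triggers one, and keep the unstratified difference as a sensitivity analysis.

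The quantity estimated remains the absolute difference in 28-day ventilation-free survival. With 8% loss to follow-up assumed, there is a side benefit: censoring need be independent only within severity level. The cost is a few lines of protocol and SAP wording before unblinding. The stratum is already recorded in order to randomize, and neither sample size nor data collection changes.
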